3.1.1.1 Definition of Dose-Limiting Toxicity

Any one of the following events will be considered a DLT if it occurs during the DLT assessment window and is assessed by the investigator to be related or possibly related to cobimetinib (rules for attributing causality are defined in Section 5.3.4):

- Grade ≥ 4 neutropenia (ANC $< 0.5 \times 10^9/L$) lasting > 7 days
- Grade ≥ 4 neutropenia with documented infection
- Febrile neutropenia, defined as ANC $< 500/mm^3$ with a single temperature of $> 38.3^\circ C$ ($101^\circ F$) or a sustained temperature of $\geq 38^\circ C$ ($100.4^\circ F$) for more than 1 hour
- Grade ≥ 4 (i.e., life threatening) anemia of any duration

- Grade ≥ 4 thrombocytopenia lasting > 48 hours or any thrombocytopenia requiring a platelet transfusion, with the following exception:
 - For patients who have undergone autologous stem cell transplant or ^{131}I -metaiodobenzylguanidine (MIBG) therapy, Grade ≥ 4 thrombocytopenia lasting > 7 days or any thrombocytopenia requiring a platelet transfusion on two or more separate dates will be considered a DLT.
- Grade ≥ 3 thrombocytopenia with bleeding
- Elevation of serum hepatic transaminase (ALT or AST) $\geq 5 \times$ the upper limit of normal (ULN)
 - For patients with elevated hepatic transaminase levels at baseline as a result of liver metastases, hepatic transaminase $\geq 5 \times$ baseline and $< 10 \times$ baseline for > 3 days, or any hepatic transaminase $\geq 10 \times$ baseline, will be considered a DLT.
- Elevation of serum bilirubin $\geq 3 \times$ ULN
- For patients reliably able to report visual symptoms: Grade ≥ 2 visual disturbance that does not resolve to Grade ≤ 1 within 72 hours after interruption of cobimetinib treatment
- Retinal pathology of any grade, or Grade ≥ 2 uveitis or iritis
- Grade ≥ 2 hemorrhage of any type
- Intracranial hemorrhage of any grade
- Grade ≥ 4 CPK elevation
- Rhabdomyolysis of any grade
 - Rhabdomyolysis includes elevations of CPK in conjunction with either clinical features (such as muscle pain, signs of renal failure, dark red or brown urine) or with laboratory evidence of renal insufficiency (including Grade 2 or higher increased creatinine or creatinine clearance [or radioisotope glomerular filtration rate] < 70 mL/min/1.73 m²), or investigator judgment that a clinical scenario is consistent with rhabdomyolysis.
- Grade ≥ 2 ventricular dysfunction or symptomatic congestive heart failure

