- Reduction in left ventricular ejection fraction (LVEF) below 50% (or shortening fraction below 28%) AND either symptomatic heart failure or a $\geq 10\%$ relative reduction from baseline measurement
 - Note: The relative reduction must be $\geq 10\%$ of baseline function, not an absolute decrease of ≥ 10 percentage points.
- Grade ≥ 4 (i.e., life threatening) vomiting or diarrhea of any duration

- Grade ≥ 3 non-hematologic, non-hepatic, non-ocular adverse event, with the following exceptions, which will not be considered DLTs:
 - Grade ≥ 3 diarrhea or rash that resolves to Grade ≤ 2 within 7 days after interruption of cobimetinib treatment.
 - Grade 3 fever.
 - Grade 3 mucositis or stomatitis that resolves to Grade ≤ 2 within 3 days.
 - Grade ≥ 3 nausea or vomiting that responds to standard-of-care therapy within 3 days.
 - Grade 3 fatigue lasting ≤ 3 days.
 - Grade 3 laboratory abnormalities that are asymptomatic and considered by the investigator not to be clinically significant.

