In order to minimize safety risks during dose escalation but to ensure optimal access for children to the trial, dose escalation will commence according to the rolling 6 design. In this design, up to a maximum of 6 patients can be enrolled concomitantly at the same dose level. The dose level allocated to a new patient is based on the number of patients currently enrolled and evaluated, the number of patients experiencing DLT, and the number of patients whose evaluation is pending at the time of new patient entry. De-escalation occurs when two or more DLTs occur at a dose level, whereas escalation can be performed when 3/3, 4/4, 5/5, 5/6, or 6/6 patients are evaluated without a DLT. Otherwise, patients can be included at the same level up to a total of 6 patients per dose level. Dose escalation will proceed according to the rules shown in [Table 1](#) (adapted from Doussau et al. 2012 and Skolnik et al. 2008).

Table 1 Dose Determination for the Next Patient in Rolling 6 Design

Number of Patients Enrolled	Number of Patients with DLTs	Number of Patients without DLT	Number of Patients with Data Pending	Enrolling Dose Level (MTD Not Exceeded)	Enrolling Dose Level (MTD Previously Exceeded)
2	0,1	Any	Any	Same	
2	2	0	0	Dose decrease	
3	0	0,1,2	3,2,1	Same	
3	0	3	0	Dose increase	
3	1	0,1,2	2,1,0	Same	
3	≥2	Any	Any	Dose decrease	
4	0	0,1,2,3	4,3,2,1	Same	Same
4	0	4	0	Dose increase	Same
4	1	0,1,2,3	3,2,1,0	Same	Same
4	≥ 2	Any	Any	Dose decrease	Dose decrease
5	0	0,1,2,3,4	5,4,3,2,1	Same	Same
5	0	5	0	Dose increase	Same
5	1	0,1,2,3,4	4,3,2,1,0	Same	Same
5	≥2	Any	Any	Dose decrease	Dose decrease
6	0	0,1,2,3,4	6,5,4,3,2	Suspend	Suspend
6	0	5,6	1,0	Dose increase	MTD
6	1	0,1,2,3,4	5,4,3,2,1	Suspend	Suspend
6	1	5	0	Dose increase	MTD
6	≥2	Any	Any	Dose decrease	Dose decrease

MTD=maximum tolerated dose.

Notes: Same=next patient would be treated at the same dose.

Dose increase=next patient would be treated at a higher dose.

Dose decrease=next patient would be treated at a lower dose.

Suspend=enrollment will be suspended until enough patients have been evaluated.

Dose escalation will proceed according to [Table 1](#) and in accordance with the rules listed below.

- If 2 or more of the first 6 DLT-evaluable patients in a cohort experience a DLT, the MTD will have been exceeded; subsequent patients must be treated at a lower dose level.

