5.1.1 Management of Specific Adverse Events

Guidelines for managing specific adverse events are provided in [Table 2](#). Asymptomatic declines in left ventricular ejection fraction should be managed according to the algorithm presented in [Table 3](#) in Section [5.1.2.1](#).

If dose reduction is indicated for an individual patient, the dose should be reduced to the next lower dose level, with dose defined in [Appendix 10](#). The dose regimen of adult patients (≥ 18 years of age) treated with the adult-recommended daily dose of 60 mg will be reduced by one 20 mg tablet (i.e., from 60 mg to 40 mg). If the patient is treated at the lowest defined dose level, the dose should be reduced by 25%. Note that the need for dose reduction below the minimum doses for administration in this study (specified in [Appendix 10](#)) is considered unacceptable toxicity and requires study drug discontinuation. For patients taking tablets, study drug should be discontinued if required weekly dose after reduction is < 60 mg/week. For patients taking suspension, study drug should be discontinued if required dose after reduction is < 4.8 mg (1 mL) daily. Dose re-escalation is not allowed.

Table 2 Guidelines for Management of Specific Adverse Events

Event	Action to Be Taken

Grade ≥ 2 diarrhea
	
Grade ≥ 3 diarrhea
 
 • If Grade ≥ 3 diarrhea occurs despite adequate supportive care, do not administer cobimetinib until recovery to Grade ≤ 1. • Following recovery, resume cobimetinib at a dose corresponding to a reduction of one dose level. • If patient experiences two episodes of Grade ≥ 3 diarrhea despite adequate supportive care, discontinue cobimetinib permanently. 
Grade 2 diarrhea
 
 • If Grade 2 diarrhea persists for ≥ 10 days despite adequate supportive care, do not administer cobimetinib until recovery to Grade ≤ 1. • Following recovery, resume cobimetinib at a reduced dose after consulting with the Medical Monitor.

Any rash with concurrent signs or symptoms strongly suggestive of a severe Type I hypersensitivity or anaphylactic or anaphylactoid reaction, with painful desquamation or mucosal involvement suggestive of Stevens-Johnson syndrome or toxic epidermal necrolysis, or with other life-threatening complications
	
 • Discontinue cobimetinib permanently. • Immediately consult a dermatologist.

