In the Phase III Study GO28141, a randomized, placebo-controlled trial comparing cobimetinib plus vemurafenib versus placebo plus vemurafenib in adult patients with advanced BRAF V600-mutated melanoma, diarrhea was the most common adverse event reported. Diarrhea events of all severity grades were reported in 59.9% of patients and Grade 3 or 4 events were reported in 6.5% of patients treated with cobimetinib plus vemurafenib versus 30.9% and 0.8% in the patients treated with placebo plus vemurafenib. No Grade 5 events of diarrhea have been reported. Serious adverse events of diarrhea were reported in 1.2% of patients treated with cobimetinib plus vemurafenib.

Nausea and vomiting have been reported in association with cobimetinib. Most nausea and vomiting events were considered non-serious and low-severity grade. In the Phase III Study GO28141, nausea and vomiting events were reported more frequently in the cobimetinib plus vemurafenib arm than the placebo plus vemurafenib arm (nausea 39.0% vs. 23.8%; vomiting 21.3% vs. 12.1%). However, of patients treated with cobimetinib plus vemurafenib, few experienced Grade 3 events (nausea 0.8%, vomiting 1.2%).

In the Phase I single agent study MEK4592g, all grades of nausea and vomiting were reported as 33.9% for both, with 0.9% reported for Grade ≥ 3 nausea and none reported for vomiting.

The combination of diarrhea, nausea, and vomiting has the potential to contribute to clinically significant volume depletion/dehydration from the combination of fluid losses with decreased oral intake. In the majority of cases, diarrhea has been effectively managed with antidiarrheal agents and supportive care.

Patients and their parents should be instructed to promptly contact the investigators if the patient develops diarrhea. Investigators should treat diarrhea and intervene promptly for patients who appear to be at increased risk of development of significant

dehydration, electrolyte imbalances, and/or multi-organ failure. Patients should receive maximum supportive care per institutional guidelines.

Guidelines for management of patients who develop Grade ≥ 2 diarrhea are provided in [Table 2](#) in Section [5.1.1](#).

Cutaneous Squamous Cell and Basal Cell Carcinoma

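### Short-lived Grade 4 diarrhea or vomiting is a DLT under one bullet and exempt under the next; cap both exceptions at Grade 3

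*Combined protocol and SAP*

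**What the plan says.** Section 3.1.1.1 opens its list with "Any one of the following events will be considered a DLT if it occurs during the DLT assessment window", subject to the investigator judging the event related or possibly related. Two consecutive bullets matter here.

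- **Specific bullet.** Grade ≥ 4 gastrointestinal events are DLTs: "i.e., life threatening) vomiting or diarrhea of any duration".
- **General bullet.** Grade ≥ 3 events that are not hematologic, hepatic or ocular are DLTs, "with the following exceptions, which will not be considered DLTs". One exception is Grade ≥ 3 diarrhea or rash that falls to Grade ≤ 2 "within 7 days after interruption of cobimetinib treatment". Another is Grade ≥ 3 "nausea or vomiting that responds to standard-of-care therapy within 3 days".

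The other exceptions under the general bullet (fever, mucositis or stomatitis, fatigue, laboratory abnormalities) apply to Grade 3 only.

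Section 3.1.1.2 applies the count: "De-escalation occurs when two or more DLTs occur at a dose level". Section 5.2.4 only refers back to Section 3.1.1.1, the synopsis does not repeat the DLT list, and Table 2 in Section 5.1.1 governs dosing, not DLT status.

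**The concern.** For the specific bullet, how long the event lasts is irrelevant. For the two exceptions, it decides the matter. A Grade 4 episode that settles quickly meets both, and the wording that exempts it is categorical: it says these events are not DLTs, not merely that they fall outside the general bullet.

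Estimating the maximum tolerated dose (MTD) and characterizing DLTs are part of the primary objective (Section 2.1). The tablet MTD, or maximum administered dose, also limits the suspension starting dose (Section 3.1.1) and caps the pediatric expansion dose (Section 3.1.2). The events are foreseeable. Diarrhea was the most common adverse event in the adult Phase III combination study (Section 5.1.2.3), and Section 4.4.1 bars prophylactic anti-emetics and anti-diarrheals during the DLT window in the escalation stage.

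What is at stake is mainly the cohort count. The patient's own dose is largely protected, because Table 2 generally says to "resume cobimetinib at a dose corresponding to a reduction of one dose level" after recovery from Grade ≥ 3 diarrhea or other related Grade ≥ 3 non-hematologic toxicity. That protection is not complete: the diarrhea entry applies when the event occurs despite adequate supportive care, whereas Section 3.1.1 bars a return to full dose after any DLT.

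**Working it through.** **1. Which reading fits the text?**

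| Grade 4 event | Specific bullet | General bullet with exceptions |
|---|---|---|
| Diarrhea, Grade ≤ 2 within 7 days of interruption | DLT | Not a DLT |
| Diarrhea, not resolved in that time | DLT | DLT |
| Vomiting, responds within 3 days | DLT | Not a DLT |
| Vomiting, does not respond | DLT | DLT |

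The bullets disagree only in rows 1 and 3. In rows 2 and 4 the general bullet already gives a DLT, so the specific bullet adds something only if it prevails in rows 1 and 3. The opening sentence makes any single bullet sufficient. Both points favour counting the event.

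**2. Effect on one cohort (Table 1, Section 3.1.1.2).** With one patient reclassified as a DLT:

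- 1/6 becomes 2/6: from a dose increase (or declaring the MTD, if it was previously exceeded) to a dose decrease.
- 0/3 becomes 1/3: from a dose increase to staying at the same dose.

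**3. Average effect.** The plan states no figure to reproduce. Let p be the per-patient DLT probability. The baselines of 15% and 20% from other causes, and the 1, 3 and 5 points added by the disputed events, are assumptions.

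Decisions in the rolling 6 design depend on enrollment timing, so two simple cases are used.

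- A: escalate on 0/3, or on 1/3 followed by 0/3. P(escalate) = (1−p)³ + 3p(1−p)⁵
- B: six patients enrolled before any decision, escalate on at most one DLT. P(escalate) = (1−p)⁶ + 6p(1−p)⁵

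Example for A at p = 0.15: 0.614 + 3 × 0.15 × 0.444 = 0.814.

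| Other-cause risk | Added points | p | A | B |
|---|---|---|---|---|
| 15% | 0 | 0.15 | 0.814 | 0.776 |
| 15% | 1 | 0.16 | 0.793 | 0.753 |
| 15% | 3 | 0.18 | 0.752 | 0.704 |
| 15% | 5 | 0.20 | 0.709 | 0.655 |
| 20% | 0 | 0.20 | 0.709 | 0.655 |
| 20% | 1 | 0.21 | 0.687 | 0.631 |
| 20% | 3 | 0.23 | 0.643 | 0.582 |
| 20% | 5 | 0.25 | 0.600 | 0.534 |

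The loss is about 2 points for a 1-point increment under either case. For a 5-point increment it is about 11 points under A and 12 under B.

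**4. Which increments are plausible?** The nearest figure is in Section 5.1.2.3: "Grade 3 or 4 events were reported in 6.5% of patients treated with cobimetinib plus vemurafenib", for diarrhea in adults. It combines Grades 3 and 4 and is not restricted to 28 days. For diarrhea alone to add 5 points at that rate, 5/6.5 = 77% of those events would have to be Grade 4, short-lived, related and in Cycle 1. The same section reports no Grade ≥ 3 vomiting with single-agent cobimetinib, and Grade 3 vomiting in 1.2% with the combination.

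**The case against.** The strongest reply is that the text already has a determinable answer. The exceptions are sub-items of the general bullet, the opening sentence lets any bullet suffice, and the specific bullet is phrased like the Grade ≥ 4 anemia bullet, which also disregards duration. On that view this is a wording slip. The preferred reading is indeed the right one. But the exempting words are absolute, and an investigator at any of about 30 sites could reasonably follow them.

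A second reply is central review. A life-threatening event is serious and reportable within 24 hours whatever its DLT label (Sections 5.2.2 and 5.4). The Medical Monitor makes escalation decisions with the Principal Investigators and the Internal Monitoring Committee after seeing adverse event data (Section 3.1.1.2). This makes an unnoticed misclassification less likely. It does not tell those reviewers which rule to apply.

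A third reply is that the upper end of the calculation is stretched, and that it compares universal lenient reading with universal strict reading. This largely stands. The 5-point rows show sensitivity and are not a forecast. If most readers already take the strict view, the expected effect is smaller than the table shows. Nothing in the documents shows that such an event has occurred or been misclassified.

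**Conclusion.** The contradiction is real, is in the current text, and is not resolved elsewhere. It should be corrected because it sits in the rule that feeds the primary DLT and MTD objective, and a single event can reverse a cohort decision. On average the effect is modest: roughly 2 percentage points in the chance of escalating per assumed 1-point rate of such events, with low rates the more plausible. These sizes rest on assumed baselines of 15% and 20%, assumed increments, and two simplified versions of the rolling 6 rules. The inconsistency itself rests on the wording alone.

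**What to change.** Count these events as DLTs and narrow the exceptions in Section 3.1.1.1:

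- Diarrhea: Grade 3 only, falling to Grade ≤ 2 "within 7 days after interruption of cobimetinib treatment".
- Nausea and vomiting: nausea stays at Grade ≥ 3 and vomiting is limited to Grade 3, with the same 3-day response condition.
- Rash: keep at Grade ≥ 3 as its own item. It shares the diarrhea exception but is not in the specific bullet, so capping the whole exception would also make short-lived Grade 4 rash a DLT, a change the contradiction does not call for.

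Use the same wording in guidance to sites and the Internal Monitoring Committee, and as a precaution re-check any Grade 4 diarrhea or vomiting already adjudicated in the DLT window. The cost is a short edit to two exceptions and that re-check.

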3.1.1.2 Dose-Escalation Rules

The starting dose of cobimetinib for tablets will be 0.6 mg/kg, administered to patients in the first cohort by mouth once daily on Days 1–21 of each 28-day treatment cycle. The dose will be increased by up to approximately 33% of the preceding dose level for each successive cohort, until an MTD or MAD is determined. The following doses will be considered:

Dose Level	Cobimetinib Dose ^a
-1	0.45 mg/kg
1 (starting dose)	0.6 mg/kg
2	0.8 mg/kg
3	1.0 mg/kg
4	1.33 mg/kg
5 or more	TBD

TBD = to be determined.

^a See [Appendix 10](#) for calculated doses per weight for each formulation.

Inpatient dose escalation is not allowed except in the following instance: once an MTD/MAD has been established, any patient still being treated at a dose lower than the recommended dose for expansion stage will be dose-escalated to the recommended dose at the start of the next cycle of therapy, unless prior dose reductions or treatment interruptions due to therapeutic toxicity have occurred in that patient.

Because maturity of CYP3A4 enzymes does not occur until 1 year of age (see Section 3.3.1), patients < 1 year of age will not be eligible for enrollment until a safety and PK assessment of the first 6 patients treated with suspension for at least one cycle of therapy has been conducted.

Relevant demographic, adverse event, laboratory, dose administration, and all available PK data will be reviewed prior to dose-escalation decisions and prior to initiation of suspension dose escalation, which will be made by the Medical Monitor in consultation with the Principal Investigators and the Internal Monitoring Committee (IMC).

In order to minimize safety risks during dose escalation but to ensure optimal access for children to the trial, dose escalation will commence according to the rolling 6 design. In this design, up to a maximum of 6 patients can be enrolled concomitantly at the same dose level. The dose level allocated to a new patient is based on the number of patients currently enrolled and evaluated, the number of patients experiencing DLT, and the number of patients whose evaluation is pending at the time of new patient entry. De-escalation occurs when two or more DLTs occur at a dose level, whereas escalation can be performed when 3/3, 4/4, 5/5, 5/6, or 6/6 patients are evaluated without a DLT. Otherwise, patients can be included at the same level up to a total of 6 patients per dose level. Dose escalation will proceed according to the rules shown in [Table 1](#) (adapted from Doussau et al. 2012 and Skolnik et al. 2008).

Table 1 Dose Determination for the Next Patient in Rolling 6 Design

Number of Patients Enrolled	Number of Patients with DLTs	Number of Patients without DLT	Number of Patients with Data Pending	Enrolling Dose Level (MTD Not Exceeded)	Enrolling Dose Level (MTD Previously Exceeded)
2	0,1	Any	Any	Same	
2	2	0	0	Dose decrease	
3	0	0,1,2	3,2,1	Same	
3	0	3	0	Dose increase	
3	1	0,1,2	2,1,0	Same	
3	≥2	Any	Any	Dose decrease	
4	0	0,1,2,3	4,3,2,1	Same	Same
4	0	4	0	Dose increase	Same
4	1	0,1,2,3	3,2,1,0	Same	Same
4	≥ 2	Any	Any	Dose decrease	Dose decrease
5	0	0,1,2,3,4	5,4,3,2,1	Same	Same
5	0	5	0	Dose increase	Same
5	1	0,1,2,3,4	4,3,2,1,0	Same	Same
5	≥2	Any	Any	Dose decrease	Dose decrease
6	0	0,1,2,3,4	6,5,4,3,2	Suspend	Suspend
6	0	5,6	1,0	Dose increase	MTD
6	1	0,1,2,3,4	5,4,3,2,1	Suspend	Suspend
6	1	5	0	Dose increase	MTD
6	≥2	Any	Any	Dose decrease	Dose decrease

MTD=maximum tolerated dose.

Notes: Same=next patient would be treated at the same dose.

Dose increase=next patient would be treated at a higher dose.

Dose decrease=next patient would be treated at a lower dose.

Suspend=enrollment will be suspended until enough patients have been evaluated.

Dose escalation will proceed according to [Table 1](#) and in accordance with the rules listed below.

- If 2 or more of the first 6 DLT-evaluable patients in a cohort experience a DLT, the MTD will have been exceeded; subsequent patients must be treated at a lower dose level.
- If the dose level at which the MTD is exceeded is $\geq 25\%$ higher than the preceding dose level, an intermediate dose level may also be evaluated. Otherwise, the highest dose at which fewer than 2 of 6 DLT-evaluable patients (i.e., $< 33\%$) experience a DLT will be declared the MTD.
- If the MTD is not exceeded at any dose level, the highest dose administered in this study will be declared the MAD.

Enrollment in the dose-escalation stage for a particular formulation will be stopped if at least 6 DLT-evaluable patients are treated at that formulation's MTD or MAD.

On the basis of an ongoing review of real-time safety data and available PK data, increases in dose level may be halted by the Sponsor as deemed appropriate.

3.1.2 Expansion Stage

After the MTD or MAD has been determined for a formulation, pediatric and young adult patients will be enrolled in tumor type cohorts to obtain additional safety, tolerability, and PK data, as well as any preliminary evidence of anti-cancer activity. Pediatric (< 18 years of age) patients will be treated at or below the formulation-specific MTD or MAD identified in the dose-escalation stage of this study. Young adult patients (≥ 18 years of age) will be treated at the recommended adult dose (see [Section 4.3.2](#)).

The Sponsor reserves the right to determine which formulation(s) will be taken forward into the expansion stage and whether enrollment into the expansion stage using tablets (if applicable) will proceed concurrently with or subsequent to dose-escalation for suspension. Enrollment in expansion cohorts may commence after the IMC has reviewed PK and safety data obtained in the dose escalation phase (see [Section 3.1.3](#)).

Each tumor type will be considered a distinct tumor type cohort. Different tumor type cohorts may not all enroll simultaneously. Tumor type cohorts will be chosen after IMC review, prior to inclusion in the expansion stage of the study. Chosen tumor type cohorts for the expansion stage may also include subgroups of tumor types included in the dose-escalation stage, with inclusion based on confirmed (rather than expected) RAS/RAF/MEK/ERK-pathway activation (based on local testing of sample from time of diagnosis or any subsequent timepoint prior to enrollment) with approval of medical monitor). Two phases of response assessment are planned for the expansion stage: an initial response assessment and an additional response assessment (as defined in [Table 6](#) in [Section 6.1](#)). An initial response assessment will be performed after a minimum of 10 patients, treated at the recommended dose for expansion stage, have

been enrolled in a tumor type cohort and followed for approximately 12 months, to determine whether to expand the cohort for additional response assessment. For purposes of initial response assessment, patients “treated at the recommended dose for expansion stage” includes those patients who initiate therapy at the eventual recommended dose for expansion, whether they are treated during the dose escalation stage or during the expansion stage. Patients who are dose-reduced from the recommended dose due to therapeutic toxicity will still be included for response assessment. Patients in dose-escalation who are treated below the recommended dose for expansion, and subsequently dose-escalated to the recommended dose, will not be included for response assessment.

Cohort expansion will be started once a pre-established number of responses for that tumor type are confirmed (per [Table 6](#)). A decision to pursue additional enrollment in a tumor type cohort may be approved by the Sponsor or Medical Monitor before the initial response assessment. Cohort expansion, including the number of patients needed for the additional response assessment, will take into account practical considerations (e.g., enrollment feasibility), preclinical findings, biomarker analysis, safety profiles, and any other relevant information. A study schema for the expansion stage is displayed in [Figure 2](#).

If the frequency of Grade 3 or 4 toxicities or other unacceptable toxicities at the initial dose level in the expansion stage suggest that this dose is intolerable, accrual at that dose level will be halted. Consideration will then be given to enrolling patients at a lower dose level.

The Sponsor may decide to stop enrollment of patients ≥ 18 years of age at any time during the study to ensure adequate enrollment of patients < 18 years of age. To meet study completion criteria below, the Sponsor may restrict enrollment of patients ≥ 10 years of age if too few patients < 10 years of age have been enrolled.

The Sponsor intends to stop study enrollment once all of the following criteria are met:

- The dose-escalation phase of both tablet and suspension formulations are complete
- At least 20 patients < 18 years of age have been treated with study drug
- At least one tumor type cohort has completed response assessment (either initial response assessment or additional response assessment)
- At least 10 patients < 10 years of age have been treated with study drug

Enrollment in a tumor type cohort will be stopped if any one of the following criteria is met:

[figure not shown]
- The number of patients needed for initial response assessment is reached and the number of responders does not meet the requirement for tumor type cohort expansion

- The number of patients needed for additional response assessment is reached
- The Sponsor has stopped the study

Some exceptions may apply to these general stopping rules, including but not limited to the following:

- Enrollment in the study may be stopped if enrollment has been open for more than 2 years and at least 20 patients have been treated with the study drug.
- Enrollment in a given tumor type cohort may be extended by the Sponsor if there is strong evidence of a positive efficacy signal in a slow enrolling and rare tumor type cohort, thus allowing for additional data to be collected.

Figure 2 Study Schema: Expansion Stage

Notes: All patients will receive cobimetinib orally once daily on Days 1–21 of each 28-day cycle. Cohort expansion, including the number of patients needed for the additional response assessment, will take into account practical considerations (e.g., enrollment feasibility), biomarker analysis, safety profiles, and any other relevant information.

